## 13.3 Eligibility Assessment

Randomisation can be undertaken by any appropriately trained trial team member. Determination of eligibility requires review by individual with prescribing responsibility. The name of the person providing this review must be documented within the randomisation system. Eligibility criteria are described in detail in Section 11.

Eligibility confirmation must be documented in the participant's medical notes. Details must include at a minimum who confirmed full eligibility, when this was confirmed, and when the participant was formally entered into the trial (e.g. randomisation).

## 13.4 Baseline Assessments

The medical records are source data for baseline assessments. The following information will be recorded on the electronic case report form by the attending clinician or delegate:

- Participants details (e.g. name or initials [depending on privacy requirements], NHS/CHI number [UK only] or medical records number including, date of birth, sex, ethnicity, contact details including email and phone number)
- Legal representative contact details
- Clinician details (name)
- Participant's height and weight
- COVID-19 symptom onset date
- Maximum COVID-19 severity as assessed by need for supplemental oxygen, nasal high flow oxygen, noninvasive ventilation, continuous positive airway pressure (CPAP), invasive mechanical ventilation or extracorporeal membrane oxygenation (ECMO)
- Oxygen saturations on air at time of study randomisation
- Closest routine measurement at point of enrolment of creatinine, urea, liver transaminases (ALT/AST), Creactive protein, haemoglobin, white cell counts, platelets, APPT, INR or PT, D-dimer, and serum creatine
  kinase (where available) with date of measurement. N.B. Some blood tests are only undertaken by sites if
  clinically indicated. Where clinically indicated and undertaken, results should be provided. Additional blood
  tests for research purposes only are not required.
- Pregnancy test (for women of childbearing potential)
- SARS-CoV-2 test result and date of test
- Major co-morbidities (e.g. chronic cardiac disease, chronic non-asthmatic pulmonary disease, chronic kidney disease, obesity, chronic neurological disorder such as stroke, dementia, malignancy, and liver disease)
- List of medications used to treat COVID-19 (e.g. remdesivir, dexamethasone, tocilizumab)

IRAS ID: 294861 Page **32** of **64** 

- Enrolment in CTIMP study during hospital admission (record therapeutic arm if known)
- Date of hospital admission, and date of ICU admission, if applicable
- Contraindication to the study treatment regimens (in the opinion of the attending clinician)
- Smoking status
- Residence in care home
- Functional status
- Confinement (shielding) status
- Vaccination status
- Baseline quality of life/symptom data and resource use data using 10 short questionnaires.
- Name of person completing the form
- The person completing the form will then be asked to confirm that they wish to randomise the patient and will be required to enter their name and e-mail address.

The above list incorporates the requirements of the NIHR Urgent Public Health research programme, and any future amendments to the required characteristics will be enacted.

## 13.5 Randomisation

Randomisation must only take place following provision of documented informed consent.

The secure randomisation system will confirm eligibility of patients to enter HEAL-COVID and determine which arms the participant may be randomised to. Randomisation will use permuted blocks of equal ratio to each trial arm to which the participant may be allocated.

A username and password, provided by the LCTC will be required to access the randomisation system. Designated research staff will be given access upon completion of training available on the trial website (www.heal-covid.net).

Randomisation: web access http://www.heal-covid.net

If there are any problems with the randomisation systems contact the coordinating CTU on [name], or via email to [contact]

(Note that the coordinating CTU is open from 0900–1700, Monday–Friday, excluding public holidays)

IRAS ID: 294861 Page **33** of **64** 

Following randomisation, the system will send automated emails to the following: PI at site, the person randomising and LCTC. The emails will document the name of the person randomising, the name of the person who confirmed eligibility, the participant's trial identification number, their allocation, and the date/time of randomisation for central monitoring purposes.

Where possible, participants who have opted to complete the patient reported questionnaires should not be notified of their treatment allocation until baseline questionnaires have been completed. Patients should receive their randomised treatment allocation as described in Section 12.

## 13.6 Baseline Patient Reported Outcomes

Patient-reported outcomes will be collected using the Aparito Atom5 application available for use on Android or iOS operating systems. Baseline completion will usually be in hospital, but with baseline/follow up permitted in all settings (home, hospital, care home, other). The order of administration will be standardised. Participants will be sent reminders, and both research personnel and participants will be provided with training resources to help minimise missing data. For participants who are unable to use the app (due to preference, language or other requirements) nurse interview-led completion (telephone or video conference) will be offered, with translators as required. Alternative language versions of each PRO will be provided when validated translations exist. Participants will be advised that the PRO data will not directly inform their clinical care or be reviewed by the clinical team. Proxy-completion will be permitted if the participant is unable to complete the PRO, will be documented and will be attributable by the provision of a unique onboarding code to use the application.

## 13.7 Intervention

Once the research team are made aware of the treatment allocation, participants will receive their allocated treatment from the point of hospital discharge. This will be administered as described in Section 12.

## 13.8 Schedule for Assessments and Follow-up.

All assessments and follow-up are to be conducted in line with the Schedule of Assessments below:

IRAS ID: 294861 Page **34** of **64** 

## 13.8.1 Schedule of Assessments

Procedures		Screening	Baseline	Variable frequency until week 12 **	Monthly	End of trial
Signed Consent Form		х				
Assessment of Eligibility Criteria		Х				
Review of Medical History		Х				
Review of Concomitant Medications		Х				
Participant characteristics			х			
Randomisation		Х				
Study Intervention			х			
Clinical Laboratory results^	Creatinine, Urea, ALT/AST, C- reactive protein	х				
	Haemoglobin, white cell count, platelets, D-dimer, APPT and INR or PT, serum creatine kinase, pregnancy test (if applicable)	х				
Patient reported outcomes (if applicable)	FACIT-Fatigue		х	х	Х	
	Modified MRC Dyspnoea Scale		х	х	х	
	COVID-19 core outcome measure for recovery		х	х	Х	
	Patient Health Questionnaire-2 PHQ		х	х	х	
	Generalized Anxiety Disorder-2 (GAD-2)		х	х	Х	
	PTSD Checklist (PCL-2)		х	х	х	
	EQ5D-5L		Х		х	
	Tolerability FACT-GP5		х	х	Х	
	Additional disease specific systemic symptoms		х	х	Х	
	Resource use				Х	
NHS Digital and equivalents	Routine digital data				х	Х

X) – As indicated/appropriate.

All follow-up data will be collected remotely. Participants will not be required to attend any appointments. PROs will be collected using the Aparito ATOM5 app or by telephone/video call whereby the caller will enter the data into the

IRAS ID: 294861 Page **35** of **64** 

^ most recent prior to enrolment blood results (dated), where they are available from routine clinical care. Order of PRO questionnaires will be standardised.

\*\*Highest frequency is weekly during the early stages of the study where the greatest clinical changes are anticipated

Aparito database via secure web interface with unique username and password per person. When PROs are collected weekly, there is a window of  $\pm 2$  days maximum, and when collected monthly this increases to  $\pm 7$  days.

Routine data will be collected via NHS Digital and equivalents in the devolved nations. The data collected will include information regarding mortality, hospital readmission, outpatient attendance, study treatment dispensing and resource use over the participant lifespan and beyond.

A non-study specific questionnaire (NIHR Patient Experience Questionnaire) will be completed at months 3 and 12. Participants will be provided with a link to complete the questionnaire that will direct them to the NIHR website/data collection tool. This questionnaire is about their experience of participating in research and does not evaluate the treatments being considered.

## 13.9 Intervention Discontinuation and Participant Discontinuation/Withdrawal

In consenting to the trial, participants/legal representative agree to all trial activities including administration of trial intervention and treatment and data collection. Every effort should be made to facilitate the completion of these for every recruited participant. If it is not possible to complete these activities (or it is deemed inappropriate) the reasons why should be documented. The following sub-sections describe the different levels of discontinuation/withdrawal.

For participants who lack capacity, if their legal representative withdraws consent for treatment or methods of follow-up then these activities would cease.

#### 13.9.1 Premature Discontinuation of Trial Intervention

The participants may discontinue treatment for reasons including, but not limited to:

- (i) Participant-led i.e. request by the participant / legal representative / consultee
- (ii) Unacceptable toxicity
- (iii) Intercurrent illness preventing further treatment
- (iv) Death
- (v) Clinician-led:
  - a. Any change in the participant's condition that justifies the discontinuation of treatment in the clinician's opinion
  - b. Reasons of non-adherence or non-compliance with treatment or other trial procedures
  - c. Participant meets an exclusion criterion (either newly developed or not previously recognised)

A decision by a participant (or their legal representative) that they no longer wish to continue receiving study treatment should not be considered to be a withdrawal of consent for follow-up, including patient-reported outcome assessment. However, participants (or their legal representative) are free to withdraw consent for some or

IRAS ID: 294861 Page **36** of **64** 

all aspects of the study at any time if they wish to do so. In accordance with regulatory guidance, de-identified data that have already been collected and incorporated in the study database will continue to be used.

### 13.9.2 Participant Withdrawal from Follow Up

Participants/Legal Representatives are free to withdraw from follow up at any time without providing a reason, though a reason should be recorded if one is given. Those who wish to withdraw from further follow-up will have the data collected up to the point of that withdrawal included in the analyses. The participant will not contribute further data to the study and the CTU should be informed via email to the CTU and via completion of a Withdrawal CRF to be returned to the CTU within 7 days.

If participants/Legal Representatives express a wish to withdraw from follow up, the research team at site should ascertain if this is for all elements of trial follow-up, for example participants may decide to stop completing the questionnaires but still allow routine data capture to be collected for the trial.

In the case of ongoing adverse events, participants should be given appropriate care under medical supervision until the symptoms of any adverse event resolve or the patient's condition becomes stable. Any SSARs will be notifiable to the CTU via processes detailed in Section 15 even if a participant has withdrawn from follow up.

# 13.10 End of Trial

The end of the trial is defined to be the date on which data for all participants is frozen and data entry privileges are withdrawn from the trial database. The trial may be closed prematurely by the Trial Steering Committee (TSC), on the recommendation of the Independent Data and Safety Monitoring Committee (IDSMC).

Site and closure activities will be centrally coordinated and conducted in accordance with CTU processes regardless of whether the trial closes as planned or prematurely. This includes activities such as:

- End of Trial notification to REC and MHRA
- All site data entered onto the study database, discrepancies raised and satisfactory responses received
- Quality Control checks of the Trial Master File as appropriate

IRAS ID: 294861 Page **37** of **64** 

### 14 SUB-STUDIES

A sub-study asks a separate research question from the parent protocol and does not contribute to the parent protocol's objectives, but uses all or a subset of study participants or samples. As an adaptive design, as further data emerges on complications of COVID-19, the study will explicitly retain the ability to add sub-studies and including recall studies. Ancillary studies will be optional and may require separate consent. These will require additional amendments.

# 14.1 Frequency of questionnaires

Completion of questionnaires is a challenge faced in many trials. It is important to ensure enough data is collected without over burdening participants. There is little evidence about the timing of questionnaires to ensure optimal completion. A randomised controlled trial will be embedded within HEAL-COVID to look at the impact of questionnaire frequency on questionnaire completion. Participants will be randomised to receive questionnaires at different frequencies. Participants will be randomised to receive questionnaires at either 1) weekly for 4 weeks and then monthly, or 2) weekly for 12 weeks and then monthly.

IRAS ID: 294861 Page **38** of **64** 

### 15 SAFETY REPORTING

Safety reporting in clinical trials is a legal and ethical requirement and it is imperative that all applicable requirements detailed here are followed during the trial.

HEAL-COVID will **only** report Serious Adverse Events that are believed with a reasonable probability to be due to one of the study treatments i.e. a Suspected Serious Adverse Reactions (SSAR).

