## 9.3 Secondary Outcomes

Secondary outcomes include:

- (i) Days alive and out of hospital
- (ii) All-cause mortality
- (iii) Hospital readmission after discharge from index hospital admission
- (iv) Suspected Serious Adverse Reactions

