#### 12.2 Standard of Care

Standard of care will align with contemporaneous best practice and include therapies patients would receive outside of the framework of the trial.

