## 13.2.1 Loss / Regain of capacity.

If a patient who has consented subsequently becomes unable to give informed consent, the previously obtained consent remains valid. If their legally acceptable representative raises concerns regarding their continued participation, this will prompt a reconsideration of their continued participation by the site Principal Investigator.

When consent for a participant's enrolment in the study has been provided by a legal representative and the participant then regains capacity while an inpatient at their recruiting hospital, the research team will provide the participant information sheet and request consent from the participant. Participants will be advised that consent is voluntary and they may withdraw without any detriment to their care. If they choose to continue to participate in the trial they will be requested to sign the consent form.

If a participant for whom consent has been provided by a legal representative regains capacity **after** hospital discharge, the research team will not be aware of this as there are no follow-up visits. As such it will not be possible to approach the participant to provide consent for continued participation. Participants who regain capacity remain able to withdraw from participation if they so wish, without giving a reason and without detriment to their care.

IRAS ID: 294861 Page **31** of **64** 

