# 15.2 Assessment of "Causality" - Relationship to Trial Treatment/Intervention

The assignment of the causality should be made using the definitions in the table below:

Table 2: Definitions of Causality

Relationship	Description
Unrelated	There is no evidence of any causal relationship.
Unlikely	There is little evidence to suggest there is a causal relationship (e.g. the event did not occur within a reasonable time after administration of the trial medication). There is another reasonable explanation for the event (e.g. the participant's clinical condition, other concomitant treatment).
Possibly	There is some evidence to suggest a causal relationship (e.g. because the event occurs within a reasonable time after administration of the trial medication). However, the influence of other factors may have contributed to the event (e.g. the participant's clinical condition, other concomitant treatments).
Probably	There is evidence to suggest a causal relationship and the influence of other factors is unlikely.
Almost certainly	There is clear evidence to suggest a causal relationship and other possible contributing factors can be ruled out.

IRAS ID: 294861 Page **39** of **64** 

HEAL-COVID will only report events that are assessed as being possibly, probably or almost certainly related to the trial treatment.

In making this assessment, there should be consideration of the probability of an alternative cause (for example, COVID-19 itself or some other condition preceding randomisation), the timing of the event with respect to study treatment, the response to withdrawal of the study treatment, and (where appropriate) the response to subsequent re-challenge.

If any doubt about the causality exists the local investigator should inform the LCTC who will notify the CI. If causality is not determined by the investigator, the causality is considered as related and then the Sponsor representative will add a second causality assessment. The opinion of the treating investigator will never be downgraded.

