# 15.4 Time period for Active Monitoring of Safety Events

Active monitoring of safety events experienced by trial participants will be from the period of randomisation until 30 days from last administration of IMP.

Pregnant women will be followed up until the outcome of the birth (see Section 15.5 for more information on reporting pregnancy).

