### 15.9.1 Safety Reports

Safety reports will be generated during the course of the trial which allows for monitoring of SSARs including reporting rates and SSARs by arm. The LCTC will send annual developmental safety update reports (DSURs)/Annual Progress Reports (APRs) containing a list of all SSARs to the IDSMC, MHRA and main REC. If any safety reports identify issues that have implications for the safety of trial participants, the PIs at all institutions participating in the trial will be notified.

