# 17.6 Statistical Analysis Plan

A full statistical analysis plan (SAP) will be written prior to the recruitment of the first participant. The SAP will be version controlled and changes to the SAP documented with rationale for the change. Any changes required to the SAP will be implemented by a statistician who has not had access to the trial database or seen comparative summaries of the data accrued to date.

The main features of the SAP are summarised below:

- Analysis will be by the intention to treat principle (ITT)
- Baseline characteristics will be summarized using descriptive statistics only, formal statistical comparisons will not be made
- The primary outcome will be analysed using a Cox proportional hazards model and the assumption of
  proportional hazards investigated. The primary outcome is specified as time to event, with secondary
  interpretation of hospital free survival days. The primary outcome must be interpreted in the light of the

IRAS ID: 294861 Page **46** of **64** 

secondary outcome specified as the number of days alive and out of hospital at 12 months (60 days for purposes of interim analysis).

- Secondary outcomes will be analysed where appropriate using regression models dependent on data type (binary, categorical, continuous etc.)
- Hospital outpatient attendance, speciality and reason, cause specific mortality and reasons for readmission will be summarised as per baseline characteristics
- Any subgroup analyses will be prespecified in the statistical analysis plan in light of accumulating evidence. Pre-specified subgroup analysis of the primary outcome will use the same approach to the analysis
- Point estimates will be reported together with 99% confidence intervals
- As much information as possible will be collected about the reasons for missing outcome data; this will be used to inform any imputation approaches employed in the analysis

IRAS ID: 294861 Page **47** of **64** 

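### The suspected serious adverse reaction outcome has no counterpart in standard of care, and the protocol defines no bleeding outcome alike in every arm

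*Protocol*

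**What the plan says.** Section 15 of the protocol restricts reporting to "Serious Adverse Events that are believed with a reasonable probability to be due to one of the study treatments". Section 15.2 sets the threshold: "HEAL-COVID will only report events that are assessed as being possibly, probably or almost certainly related to the trial treatment". Section 9.3 lists "Suspected Serious Adverse Reactions" as the fourth secondary outcome, and it is the only one there framed as a safety outcome. Section 15.9.1 provides for "monitoring of SSARs including reporting rates and SSARs by arm".

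Section 15.4 sets active monitoring "from the period of randomisation until 30 days from last administration of IMP". The comparator is standard of care, which section 12.2 says will "include therapies patients would receive outside of the framework of the trial". Section 10.1 makes the trial open label.

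On how sites learn of events, section 15.8 names routine study visits first, followed by the notes, the participant and other means. Section 13.2.1, on participants who regain capacity after discharge, says "the research team will not be aware of this as there are no follow-up visits". Section 13.8.1 confirms that follow-up is remote with no appointments.

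Outside the SSAR system, linked data on mortality, readmission and outpatient attendance are collected with no restriction by arm (sections 13.8.1 and 18.2). Section 17.6 states that "cause specific mortality and reasons for readmission will be summarised as per baseline characteristics". Section 12.3.1 names bleeding as the risk of this drug class and presents the choice of apixaban in terms of net benefit.

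**The concern.** An outcome that needs attribution to a study drug cannot, crossover aside, occur in an arm that receives none. If it is listed with the other secondary outcomes and tabulated by arm, a reader or the IDSMC may take the difference between columns as an estimate of harm. It is not one: background events count on active treatment when judged possibly related, and never on standard of care.

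The count can also err downwards. Sites report what they become aware of, and they have no scheduled contact with participants after discharge, so a true excess may go unreported.

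Apixaban is where this matters most. Its case rests on thrombotic benefit set against bleeding, and the protocol defines no bleeding outcome that reads the same in both arms of that comparison.

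**Working it through.** **1. The plan's own figures.** The protocol gives no safety figure to reproduce. The figures used below, 877 per arm and the 1% level, come from section 17.2, so that calculation was checked. Schoenfeld's formula with hazard ratio 1.5, two-sided 1% and 90% power gives 363 events against 362 stated. Power at 362 events for hazard ratios 1.30 to 1.50 comes to 46.8, 61.0, 73.4, 83.1 and 90.0%, against 47.0, 61.1, 73.5, 83.2 and 90.0% in the protocol's table. No stated number is wrong. The point is structural.

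**2. Can the outcome occur in each arm?**

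| Element of the SSAR outcome | Apixaban | Atorvastatin | Standard of care |
|---|---|---|---|
| Study treatment to attribute to (15, 15.2) | yes | yes | none |
| Window, counted from first dose (15.4 with 12.3.2, 12.4.2) | 14 + 30 = 44 days | 12 months + 30 days, about 13 months | undefined |
| Assessor knows the allocation (10.1) | yes | yes | yes |

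The window starts at randomisation and treatment starts at discharge, so the true length is slightly greater. It also shortens for a participant who stops early, so it depends on adherence after randomisation as well as on arm.

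**3. How far could the table mislead?** The protocol gives no bleeding rate, so these rates are assumptions. Let serious bleeding have the same true rate q in both arms, and let every case on apixaban be judged at least possibly related. The expected active-arm count is 877 × q, and the standard-of-care count is 0 by definition. With equal arms, the two-sided p-value for x against 0 is close to 2 × 0.5^x. For x = 6 that is 0.031, and for x = 5 it is 0.063, so six or more would look nominally significant at 5%.

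| Assumed q, both arms | Expected SSARs, apixaban v standard of care | P(6 or more), binomial |
|---|---|---|
| 0.5% | 4.4 v 0 | 28% |
| 1% | 8.8 v 0 | 87% |
| 2% | 17.5 v 0 | above 99% |

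At 9 of 877 against 0 of 877, Fisher's exact test gives p = 0.0038. If only half the events are attributed or reach the site, the expected counts halve: the 1% row then behaves like the 0.5% row. If sites hear of none, the table reads 0 v 0 whatever the truth.

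**4. What is measured alike in all arms?** The primary outcome is re-hospitalisation or death from any cause. Section 9.3 adds all-cause mortality, readmission, and days alive and out of hospital. Section 17.6 has causes of death and reasons for readmission summarised, as baseline characteristics are: descriptively and without formal comparison. Bleeding can therefore be seen in every arm, but with no stated definition, window or estimate.

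**5. What would a common outcome deliver?** With 1% in both arms, the standard error of the difference is √(2 × 0.01 × 0.99 / 877) = 0.475 percentage points. The 99% interval is then about ± 2.576 × 0.475 = ± 1.2 points. Power to detect 1% v 2% is about 41% at two-sided 5% and 20% at 1%. For 1% v 3% it is about 85% and 66%.

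**The case against.** A reader might infer that safety is captured only through SSARs, and that apixaban bleeding therefore cannot be weighed against benefit. The documents do not support that. Section 15 limits what sites report, not what the trial collects. A post-discharge bleed that leads to admission or death is a primary-outcome event in every arm, so hospital-free survival sets such bleeding against thrombotic benefit under intention to treat. Site-known deaths are notified whether related or not (section 15.6), and FACT-GP5 records tolerability. Under section 17.4 the IDSMC sees analyses of the accumulating data at least monthly and may stop an arm for safety at any time. All of this stands.

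Two further objections also stand. Reporting only SSARs from sites is a reasonable choice for marketed, repurposed drugs in a pragmatic trial and is not itself the error. And no test of SSARs against standard of care is planned, so 9 v 0 is an illustration on assumed rates, not a result the plan would produce.

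It can also be said that code lists and windows belong in the SAP, which is not shown and may define bleeding from routine data. This answers the point only in part. The outcome list, the window tied to the last dose and the descriptive handling of causes are all fixed in the protocol. A composite of 362 all-cause events measures the net effect, but a handful of bleeds cannot be separated out within it.

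**Conclusion.** The point holds in a limited form. The SSAR secondary outcome is not comparable with standard of care: it requires attribution to a study treatment, is judged with allocation known, and uses a window that differs between the active arms and does not exist for control. This follows from the text and needs no assumption beyond negligible crossover.

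Net effect is measured, because bleeds that cause readmission or death enter the primary outcome in all arms. What the protocol lacks is a bleeding outcome defined identically across arms. Bleeds that lead to neither admission nor death are seen only in part, through outpatient specialty and reason.

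The size of the distortion depends on rates the protocol does not give. Across assumed equal true rates of 0.5 to 2% with full attribution, the table would show about 4 to 18 SSARs against 0 with no true difference; under-reporting by sites would pull this towards 0 v 0. This is worth correcting before analysis, but it does not undermine the primary comparison.

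**What to change.** 1. Present SSARs as a listing for active arms only, and remove them from section 9.3 as a between-arm outcome. Expedited reporting is unaffected.
2. Add to section 9.3 a secondary safety outcome of hospitalisation or death with a bleeding code, from the linked data already obtained, with liver- or muscle-injury codes for the atorvastatin comparison. Define it identically in each arm over one fixed window from randomisation. Estimate the difference by intention to treat within each comparison, with a 99% confidence interval to match section 17.6, and include it in the IDSMC reports.
3. Reconcile the reference to routine study visits in section 15.8 with the statements in sections 13.2.1 and 13.8.1 that there are none.

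The cost is a code list and one extra analysis, with no new data collection. Routine coding is less specific than adjudication and arrives with a lag. Precision for rare events will be low, as the interval of about ± 1.2 points at an assumed 1% rate shows, so the result should be read as an estimate with its interval rather than as a test.
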